3. STUDY PLAN AND PROCEDURES

This study will be conducted at Tufts Medical Center in Boston, MA. No study-related procedures will be conducted at Northeastern University.

3.1 Overall study design and study flow chart

Drug Substance: Movantik
Study Number: ESR-15-11000
Tufts IRB #12043
Version: Protocol version #19
Date: September 10, 2018

This will be a Phase II, proof of concept, single-center, randomized, double-blind, placebo-controlled pilot study to assess the efficacy and safety of naloxegol for preventing lower GI tract paralysis in 36 (18 naloxegol; 18 placebo) medical critically ill adults who require scheduled IV opioid therapy.

Drug Substance: Movantik
 Study Number: ESR-15-11000
 Tufts IRB #12043
 Version: Protocol version #19
 Date: September 10, 2018

Table 1. Study Plan

Study period	ICU admission and initiation of scheduled opioid	Treatment Period (maximum of 10 days)										Study drug stopped or early termination	Discharge from ICU	
		1	2	3	4	5	6	7	8	9	10			
Study day	Maximum of 72 hrs to enroll patient													
Screening	√													
Randomization		√												
Use of study laxative guideline		√	√	√	√	√	√	√	√	√	√			
Administration of study medication		√	√	√	√	√	√	√	√	√	√			
Baseline demographic information	√	√												
Inclusion/Exclusion criteria	√													
Pregnancy test for WOCBP	√													
Efficacy outcomes														
Monitoring that is a routine part of care at Tufts MC														
Bedside nurse														
Documentation of all SBMs	√	√	√	√	√	√	√	√	√	√	√			
Volume of enteral nutrition administered		√	√	√	√	√	√	√	√	√	√			
Fluid balance		√	√	√	√	√	√	√	√	√	√			
Sedation assessment SAS (q6h)		√	√	√	√	√	√	√	√	√	√			
Pain assessment (numerical rating q6h)	√	√	√	√	√	√	√	√	√	√	√			
Delirium assessment (ICSDC q12h)		√	√	√	√	√	√	√	√	√	√			
Investigative team														
Documentation of study laxative guideline use		√	√	√	√	√	√	√	√	√	√			
% of daily enteral nutrition goal achieved		√	√	√	√	√	√	√	√	√	√			
Daily opioid requirements	√	√	√	√	√	√	√	√	√	√	√			
Daily sedative requirements		√	√	√	√	√	√	√	√	√	√			

Drug Substance: Movantik
 Study Number: ESR-15-11000
 Tufts IRB #12043
 Version: Protocol version #19
 Date: September 10, 2018

Serum creatinine to calculate creatinine clearance	√	√	√	√	√	√	√	√	√	√	√	√	
Monitoring that is not a routine part of care at Tufts MC													
Bedside nurse													
Characterization of each SBM for size		√	√	√	√	√	√	√	√	√	√	√	
Characterization of each SBM using the Bliss Scale		√	√	√	√	√	√	√	√	√	√	√	
Measurement of bladder pressure in subjects with a foley catheter in place for a clinical reason (to estimate abdominal pressure) q8h		√	√	√	√	√	√	√	√	√	√	√	
Investigative team													
Requirement for mechanical ventilation	√	√	√	√	√	√	√	√	√	√	√	√	
SOFA score calculation (daily)		√	√	√	√	√	√	√	√	√	√	√	
Occurrence of lower GI tract paralysis requiring a GI or surgical consult		√	√	√	√	√	√	√	√	√	√	√	
Safety outcomes													
Monitoring that is a routine part of care at Tufts MC													
Bedside nurse													
Presence of diarrhea	√	√	√	√	√	√	√	√	√	√	√	√	
Investigative team													
Presence of a diaper or rectal tube		√	√	√	√	√	√	√	√	√	√	√	
Monitoring that is not a routine part of care at Tufts MC													
Bedside nurse													
Characterization of diarrhea using the Bristol Scale		√	√	√	√	√	√	√	√	√	√	√	
Evaluation for opioid withdrawal using the COWS scale before and 2 hours after each daily study dose		√	√	√	√	√	√	√	√	√	√	√	

Additional assessments not included in table:

1. Baseline demographics [age, gender, APACHE II score, Charlson comorbidity scale score, primary reason for ICU admission (based on APACHE III criteria)], baseline comorbidities potentially associated with an increased risk for lower gastrointestinal tract paralysis, treatments

Drug Substance: Movantik
Study Number: ESR-15-11000
Tufts IRB #12043
Version: Protocol version #19
Date: September 10, 2018

received at the time of ICU admission or administered after ICU admission that might influence SBM frequency and/or lower gastrointestinal tract paralysis incidence, and primary reason(s) for scheduled opioid initiation.

2. Evaluation for adverse events

Impact of Level of Sedation on Patient Assessments: Patients admitted to the Medical ICU at Tufts MC are generally maintained in an awake or lightly sedated state. For a patient who may require a short period of deeper sedation all of the following assessments above will be able to be still evaluated/collected **except:** COWS

Drug Substance: Movantik
Study Number: ESR-15-11000
Tufts IRB #12043
Version: Protocol version #19
Date: September 10, 2018

3.2 Rationale for study design, doses and control groups.

There are many potential sources of bias in study that investigating the efficacy of safety of naloxegol for the prevention of lower GI tract paralysis in critically ill adults and thus a double-blind, placebo-controlled study is the gold standard study design to use. There is no reason to suggest that a dose of greater than 25mg daily of naloxegol (the current FDA-approved dose for the treatment of opioid induced constipation) is not the appropriate dose for this pilot investigation. As outlined in the current package insert, the study dose will be reduced to 12.5mg daily when patients are concomitantly administered a moderate CYP314 inhibitor or who have renal dysfunction (calculated creatinine clearance \leq 60 ml/min). Given that this is a randomized study, the treatment and control groups should be identical. Initiation of docusate 100mg twice daily is a standard of practice in all patients receiving an opioid who are admitted to the medical ICU service at Tufts Medical Center. Given that it remains unknown if naloxegol is efficacious in preventing lower GI tract paralysis in critically ill adults and that half the patients will be administered placebo, all patients will be managed with an aggressive standardized laxative protocol that is based on the most common clinical practices in the ICUs at Tufts Medical Center.

4. SUBJECT SELECTION CRITERIA

The investigators will maintain a screening log for the duration of the study.

Each patient will meet all of the inclusion criteria and none of the exclusion criteria. A study screening sheet will be completed by a member of the investigative staff and confirmed by a second member of the investigation staff before randomization will occur.

All patients consecutively admitted to the medical ICU service who are admitted to the MICU, CCU, SICU or NCCU at Tufts Medical Center will be screened on a daily basis (through review of the ICU admission note, available laboratory data, the medication administration record, and the patient flowsheet by one of the study investigators who will determine if the patient meets all inclusion and exclusion criteria for participation in the study).

When the patient is found to meet all inclusion and no exclusion criteria, and Drs. [name], [name] or [name] have reviewed and signed the screening form, and the patient's primary ICU attending has approved their enrollment, the subject/legally authorized representative will be approached (either in person or by phone (ie. invited to come to Tufts MC to discuss the study) during the periods of 7am to 7pm.

4. 1. Inclusion criteria

- a. Admitted to the medical ICU service.
- b. Age \geq 18 years.
- c. Expected by the medical ICU attending physician to require admission to the MICU service for \geq 48 hours.
- d. Intravenous opioid administration in the prior 24 hours of \geq 100 mcg fentanyl equivalents (including both scheduled and "as needed" therapy).

Drug Substance: Movantik
Study Number: ESR-15-11000
Tufts IRB #12043
Version: Protocol version #19
Date: September 10, 2018

e. No objections from the MICU or attending physician for enrollment.

4.2 Exclusion criteria

- a. Scheduled use of morphine, oxycodone, hydromorphone, fentanyl \geq 100 mg morphine equivalents per day in the week prior to ICU admission as evaluated by medical record review and/or interview with patient and/or family.
- b. Scheduled use of methadone at any dose in the week prior to ICU admission as evaluated by medical record review and/or interview with patient and/or family.
- c. History of constipation (as defined by the scheduled use of bisacodyl, senokot, lactulose, PEG 3350 (Miralax) and/or Fleet enema) prior to ICU admission as evaluated by medical record review and/or interview with patient and/or family.
- d. Current scheduled use a medication affecting gastric motility (i.e., metoclopramide, domperidone, erythromycin and loperamide).
- e. Current use of medication known to be a strong CYP3A4 inhibitor (itraconazole, lopinavir/ritonavir, clarithromycin, ritonavir, ketoconazole, indinavir/ritonavir, voriconazole, nefazodone).
- f. Current use of a medication known to be a strong CYP3A4 inducer (rifampin, carbamazepine, St. John's Wort).
- g. Known serious or severe hypersensitivity to naloxegol (Movantik) or any of its excipients.
- h. Patients admitted with a history of a neurologic condition that may affect the permeability of the blood-brain barrier (e.g. multiple sclerosis, recent brain injury, Alzheimer's disease, uncontrolled epilepsy, acute stroke, acute meningitis).
- i. Patients admitted with an acute GI condition (e.g., clinical evidence of acute fecal impaction/complete obstruction, acute surgical abdomen, acute GI bleeding).
- j. Patients with a condition affecting GI motility or function (e.g. inflammatory bowel disease requiring immunosuppressive therapy, symptomatic Clostridium difficile, active diverticular disease, surgery on the colon or abdomen within 60 days of ICU admission).
- k. Patients with underlying cancer who are at heightened risk of GI perforation such as those with underlying malignancies of the GI tract or peritoneum, recurrent or advanced ovarian cancer, vascular endothelial growth factor inhibitor treatment.
- l. Current use of total parenteral nutrition
- m. Administration of enteral nutrition through a jejunum tube.
- n. Severe hepatic dysfunction

Drug Substance: Movantik
Study Number: ESR-15-11000
Tufts IRB #12043
Version: Protocol version #19
Date: September 10, 2018

[Defined as either: i. INR ≥ 2.0 (not related to warfarin therapy) AND total bilirubin ≥ 2 or ii. Diagnosis of liver cirrhosis as defined by Child-Pugh classes B or C or iii. acute liver disease is the primary reason for admission to the ICU.]

- o. Inability to enroll in study and initiate study medication within 72 hours of the patient being first initiated on IV opioid therapy after ICU admission.
- p. Unreliable method for enteral, gastric and/or oral medication administration (e.g., no feeding tube, NG tube is on suction).
- q. Current or previous use of an opioid antagonist agent (e.g., naloxogel, methylnaltrexone) agent in the past 30 days.
- r. Patients expected to expire within 24 hours.
- s. Pregnant or actively lactating females.
- t. Current participation in another interventional clinical study.
- u. Inability to obtain informed consent from either the subject or their legally authorized representative.

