Patients taking a strong CYP3A4 inhibitor are excluded from the study. If there is a clinical need to use a strong CYP3A4 inhibitor medication (and another therapeutic option without these properties is not available) then the subject will be removed from the study.

- c. In the package insert, it is stated that naloxegol is contraindicated in patients concomitantly taking strong CYP3A4 inducers (e.g. rifampin, carbamazepine, St. John's Wort) as it could significantly decrease plasma naloxegol concentrations and may decrease the efficacy of naloxegol (Movantik).

The following steps have been taken in the protocol to minimize the risk for this effect. Patients taking a strong CYP3A4 inducer are excluded from the study. If there is a clinical need to use a strong CYP3A4 inducer medication (and another therapeutic option without these properties is not available) then the subject will be removed from the study.

- d. Cases of gastrointestinal perforation have been reported with the use of another peripherally acting mu opioid receptor antagonist (PAMORA) when used in patients who have a diffuse or local reduction in the structural integrity in the wall of the gastrointestinal tract.

The following steps have been taken in the protocol to minimize the risk for this adverse effect. The following patients are excluded from the study: i. admitted with an acute GI condition (e.g., clinical evidence of acute fecal impaction/complete obstruction, acute surgical abdomen, acute GI bleeding), ii. having a condition affect affecting GI motility or function (e.g. inflammatory bowel disease

Drug Substance: Movantik
Study Number: ESR-15-11000
Tufts IRB #12043
Version: Protocol version #19
Date: September 10, 2018

requiring immunosuppressive therapy, symptomatic Clostridium difficile, active diverticular disease, surgery on the colon or abdomen within 60 days of ICU admission or iii. having a history of constipation at the time of ICU admission.

- e. The effect of severe hepatic impairment (e.g. Cirrhosis with a Child-Pugh Class scale score of B or C) on the pharmacokinetics of naloxegol has not been evaluated.

The following steps have been taken in the protocol to minimize the risk for this adverse effect:
Patients with severe hepatic impairment are excluded from the study.

- f. Naloxegol has been very rarely associated with signs of opioid withdrawal.

The following steps have been taken in the protocol to minimize the risk for this adverse effect:

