- i. Patients having an acute disruption of the blood brain barrier (that could potentiate naloxegol absorption to the CNS) are excluded from the study.
- ii. Patients taking scheduled opioids at the time of ICU admission are excluded.
- iii. Each study patient will be carefully monitored before and 2 hours each study dose for signs of opioid withdrawal using the Clinical Opioid Withdrawal Scale (COWS) score.

- g. No data regarding use of naloxegol in pregnancy and its use in a pregnant female taking opioids may precipitate opioid withdrawal in the infant.

The following step has been taken in the protocol to minimize the risk for this adverse effect. All female patients will be screened with a pregnancy test prior to study enrollment and if found to be pregnant will be excluded from the study.

- h. No data regarding use of naloxegol in lactating mothers and its use in a lactating female taking opioids may precipitate opioid withdrawal in the fetus.

The following step has been taken in the protocol to minimize the risk for this adverse effect. All lactating females will be excluded from the study.

- i. In the package insert, it is recommended that maintenance laxative therapy be discontinued before starting naloxegol and that laxative therapy should only be resumed in those patients who have OIC symptoms and after no sooner than 3 days after naloxegol was initiated.

This recommendation is based on the treatment of OIC in an outpatient setting and is not based on the usual clinical practices that are used to prevent lower GI tract paralysis in the ICU. Given that half the patients in the study will be randomized to placebo (in a blinded fashion), it is important that normal ICU lower GI tract paralysis prevention practices are incorporated into the research protocol. It is standard practice that all patients initiated on opioid therapy in the medical ICU at Tufts MC are started on scheduled docusate therapy and then managed with a step-wise laxative therapy (in a similar fashion to the laxative protocol developed for the study) as symptoms of lower GI tract paralysis develop and persist. The study laxative protocol accounts for patients who do have a SBM (i.e., laxative therapy is down-titrated/stopped), and stool softness and frequency is carefully being monitored as part of the study, so it is not expected that study patients, regardless of study

Drug Substance: Movantik
Study Number: ESR-15-11000
Tufts IRB #12043
Version: Protocol version #19

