Date: September 10, 2018

assignment, will receive a greater amount of laxative therapy than is clinically necessary to prevent lower GI tract paralysis.

j. Scheduled use of opioids (≥ 100 mg morphine equivalents per day in the week prior to ICU admission) is a study exclusion criteria. This is information may be considered sensitive information and should be carefully collected in a de-identified fashion.

During the study screening process, the patient's medical record will be reviewed to see if the patient has a history of opioid use (both prescribed and non-prescribed). In addition, at the beginning of the consent discussion, the patient (legally authorized representative) will be asked whether the patient has used an opioid in the past week. If such use is not detected (i.e., through both methods), the patient will be deemed NOT to meet this study exclusion criteria. The study screening log (where the reason(s) for patient exclusion is documented) are completed de-identified so this information regarding opioid use will remain protected. If this opioid use history information is already documented in the patient record, then the patient will be excluded from study participation and the study team will never meet with the patient/authorized representative. If this opioid use history information is not documented in the patient record, but then identified through a discussion with the patient (or legally authorized representative), it will remain in the confidence of the investigative team (ie. not provided to the medical team) and documented in a de-identified fashion only on the study screening log as an exclusion criteria.

k. Removal of urinary (foley) catheters in the ICUs at Tufts MC is an important quality improvement initiative, will a urinary catheter be used solely for research purposes and is there a risk to inserting the bladder pressure transducer into a foley catheter that is already in place?

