Appendix 10. Investigative Team Daily Data Collection Form.

IRB # 12043 Impact of Naloxegol (Movantik) on Prevention of Lower Gastrointestinal Tract Paralysis in Critically Ill Adults Initiated on Scheduled IV Opioid Therapy: A Randomized, Double-Blind, Placebo-Controlled, Phase II, Single-Center, Proof of Concept Study. PI: [name]

Subject ID: _____ Subject Initials: _____ ICU Room: _____ *Date (of day shift): _____ Study day# _____

*Note: this monitoring form goes from 0700h to 06:59h the next day

Time frame	Day Shift (0700 – 14:59h)	Afternoon shift (15:00-22:59H)	Night shift (23:00-06:59h)
Fentanyl (mcg)			
Hydromorphone (mg)			
Morphine (mg)			
Oxycodone (mg)			
Hydrocodone (mg)			
Methadone (mg)			
Other Opioids: Name and Dose			
Diazepam (mg)			
Lorazepam (mg)			
Midazolam (mg)			
Dexmedetomidine (mcg)			

Drug Substance: Movantik
Study Number: ESR-15-11000
Tufts IRB #12043
Version: Protocol version #19
Date: September 10, 2018

Propofol (mg)			
Haloperidol (mg)			
Quetiapine (mg)			
Volume of enteral nutrition administered (mL)			
Enteral nutrition goal (mL)			
% of enteral nutrition goal reached			
Fluid balance (+ or -) (mL)			
Lowest SAS			
Highest SAS			
ICDSC score (if evaluated during this shift)			
Lowest pain assessment score			
Highest pain assessment score			
Current Laxative Guideline Step (ie. 1, 2, 3 or 4)			
Laxatives administered (list all agents and doses)			
Requirement for mechanical ventilation? (Y/N)			
Presence of rectal tube? (Y/N)			

Drug Substance: Movantik
Study Number: ESR-15-11000
Tufts IRB #12043
Version: Protocol version #19
Date: September 10, 2018

(Please note time of insertion if new)			
GI or Surgical consult for lower GI tract paralysis? Y/N			
SOFA Score (worst values over study day)			
Serum creatinine (worst value over study day)			
Calculated creatinine clearance (worst value over study day)			

initials of investigational team member completing/verifying form _____ **date** _____

Daily SOFA Calculator

Pt Study ID: Pt Initials:

PP MM

Please retain this worksheet at the site with the CRF.

Calculate SOFA score using values from the 24 hour period prior to randomization.

A. Please circle appropriate score

Drug Substance: Movantik
 Study Number: ESR-15-11000
 Tufts IRB #12043
 Version: Protocol version #19
 Date: September 10, 2018

Organ System	0	1	2	3	4	Score
RESPIRATION PaO ₂ /FiO ₂ (mmHg)	>400	301-400	201-300	101-200 with respiratory support	< 100 with respiratory support	

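### Exclusion 4.2(a) names four opioids, so scheduled users of an unlisted opioid such as hydrocodone at 100 mg morphine equivalents/day or more are eligible although Section 1.4(j) says they are excluded

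*Protocol*

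**What the plan says.** Section 4 of the Protocol makes the listed criteria the enrollment rule: "Each patient will meet all of the inclusion criteria and none of the exclusion criteria". Prior opioid use is then covered by two exclusions in Section 4.2.

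- 4.2(a): "Scheduled use of morphine, oxycodone, hydromorphone, fentanyl", at 100 mg morphine equivalents per day or more in the week before ICU admission.
- 4.2(b): "Scheduled use of methadone at any dose in the week prior to ICU admission".

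Section 1.4 (Benefit/risk and ethical assessment) describes the exclusion in three further places.

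- 1.4(j), opening line: "Scheduled use of opioids (≥ 100 mg morphine equivalents per day in the week prior to ICU admission) is a study exclusion criteria".
- 1.4(j), later sentence on record review: "If this opioid use history information is already documented in the patient record, then the patient will be excluded from study participation".
- 1.4(f)(ii): "Patients taking scheduled opioids at the time of ICU admission are excluded". This is listed among the steps taken because "Naloxegol has been very rarely associated with signs of opioid withdrawal".

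The SAP does not deal with eligibility. No text in either document reconciles these statements.

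**The concern.** Section 4.2(a) is a closed list of four drugs, while 1.4(j) covers the whole class. The two give different answers for a scheduled user of an opioid that 4.2 does not name. Section 1.4(f)(ii) goes further and has no dose limit at all.

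Two things are at stake. One is who may be enrolled: staff who follow Section 4.2 exactly will admit a patient whom the protocol elsewhere calls excluded. The other is whether the benefit/risk section describes the trial accurately, because 1.4(f)(ii) is put forward as a protection against withdrawal and the enrollment rule does not fully provide it.

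**Working it through.** The plan states no figure on this point, so the check compares the texts.

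**Is the list in 4.2(a) closed?** It names four drugs, with no class term and no marker of examples. The same section marks examples with e.g. in (h), (i), (j), (p) and (q). The plain reading is that 4.2(a) covers those four drugs only, with methadone added by 4.2(b).

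**Do the statements decide cases differently?** Take hypothetical patients who use one opioid on schedule throughout the week before ICU admission and up to admission. Doses are in morphine equivalents (ME) per day.

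| Case | 4.2(a)–(b) | 1.4(j), opening line | 1.4(f)(ii) |
|---|---|---|---|
| Oxycodone, 120 mg ME | excluded | excluded | excluded |
| Hydrocodone, 120 mg ME | eligible | excluded | excluded |
| Oxycodone, 60 mg ME | eligible | not excluded | excluded |
| Methadone, 60 mg ME | excluded by (b) | not excluded | excluded |

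**Row 2** is the main gap. The drug is not named in 4.2(a) or (b), the dose is above the threshold, and 1.4(j) calls such use a study exclusion. The same holds for any other unlisted opioid at that dose. Hydrocodone is a drug the trial expects to meet in some form: it has its own line in Appendix 10 and in Appendix 11, item 18.

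**Row 3** depends on 1.4(f)(ii) alone. Section 4.2(a) and the opening line of 1.4(j) agree that 60 mg does not exclude.

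**Row 4** shows that the opening line of 1.4(j) also falls short of 4.2(b), because it applies the threshold to methadone as to any other opioid.

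**Does the screening text settle it?** Section 1.4(j) has the record checked for opioid use and has the patient or representative asked about any use in the past week. It then says that a documented history leads to exclusion. That sentence can refer back to the threshold in the opening line or can mean any documented use, so it does not decide row 2 or row 3.

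**Timing.** Section 1.4(f)(ii) refers to use at ICU admission, and 4.2(a)–(b) to the week before. The cases above meet both, so timing does not explain the differences.

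**The case against.** The strongest reply is that there is one operative rule. Section 4 governs enrollment, and Section 1.4 is a narrative that shortens criteria elsewhere too: history of constipation, severe hepatic impairment and blood-brain-barrier disruption are all spelled out only in 4.2. On this view 1.4(j) supplies the dose limit that 1.4(f)(ii) omits. For the lower-dose user this largely stands. A reader might infer that 4.2 wrongly admits patients below 100 mg per day. The documents do not support that, because two of the three statements agree on the threshold.

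The reply does not remove the gap for unlisted drugs. There the narrative is broader than the criterion, and it names its wording as a study exclusion.

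A second reply is that screening would reveal an unlisted opioid: record review and the interview are not limited to the four drugs, a second staff member confirms the screening sheet, and the attending physician approves enrollment. That is fair as to detection. It does not say whether the patient, once detected, is to be excluded.

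Four other stronger readings are tempting.

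- A reader might use the opioid lines in Appendices 10 and 11 to measure how incomplete the exclusion is. Those forms record opioids given in the ICU or current at randomization, not scheduled use before admission, so they give no such measure.
- A reader might infer that patients are left unprotected from withdrawal. The exclusions for blood-brain-barrier conditions and strong CYP3A4 inhibitors stand, and so does COWS scoring around each dose, although the notes to Table 1 say COWS cannot be assessed during deeper sedation.
- A reader might infer that screening ignores dose. The screening sheet is not in the documents, so this cannot be said.
- A reader might take the documented-history sentence in 1.4(j) to exclude every prior opioid user. It follows the threshold criterion and may simply refer back to it.

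**Conclusion.** The point holds and is minor: the exclusion is wrong as written. Under 4.2(a)–(b), a scheduled user of an unlisted opioid at 100 mg morphine equivalents per day or more is eligible, contrary to 1.4(j). In addition, 1.4(f)(ii) claims a protection without a dose limit that 4.2 does not deliver below that threshold. This is most likely loose summary wording.

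The size in patients is unknown. The documents do not say how many patients arrive on unlisted opioids at this dose, and none is estimated here. No harm is shown, and no effect on the primary test, power or sample size is claimed.

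The conclusion rests on reading 4.2(a) as a closed list, which its wording supports. The fix also assumes that the 100 mg threshold is the intended rule, as 4.2(a) and 1.4(j) both state it.

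**What to change.** 1. Reword 4.2(a) so that it excludes scheduled use of any opioid other than methadone, at 100 mg or more of morphine equivalents daily, during the week before admission to the ICU.
2. Keep 4.2(b) unchanged.
3. Correct 1.4(f)(ii), the opening line of 1.4(j) and the documented-history sentence of 1.4(j) so that each states the same rule: the threshold for all opioids, and methadone at any dose.

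The cost is amendment wording in these places, with the agreement and IRB approval that Section 8.4 requires, and a rare extra exclusion from the wider drug list. The sample size and the analysis do not change.
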